### **3.0 Inclusion and Exclusion Criteria**

#### **3.1 Screening for eligibility.**

##### **A. Recruitment**

We will randomize approximately 374 participants over approximately 36-months, allowing for a conservative 20% dropout to allow for uncertainties in the post-COVID-19 environment. We will identify participants using 1) inpatient admission list, 2) referral from providers, 3) CR consults list, and 4) approved flyers, letters, and mailings, 5) cardiology consult lists and clinics, and 6) discharge list

##### **B. Randomization**

We will use the high quality pseudo-random deviate generator in SAS® (SAS Institute, Inc., Cary, North Carolina) to randomize participants to MACRO or SOC in 1:1 ratio with random block sizes chosen from small even numbers. Exact block sizes will be revealed to the rest of the study team at the conclusion of the study to prevent educated guessing. There are some key demographic differences in populations served by the study sites, as described in the Study Settings section. Thus, randomization will be stratified by site to ensure a balance between the treatment groups with respect to site by design rather than chance. To retain maximum degree of flexibility in post-COVID-19 environment, no other stratification criterion will be employed. The statistician will create schedules which link the randomization sequence number and treatment arm and will provide them to the team constructing the data management system. At randomization, a study team member will establish the link between the participant study identifier and randomization sequence number by clicking on a database function. Randomization data will only be visible to the study statistician and intervention delivery personnel. Therefore, all personnel involved in post assessments will be blind to treatment assignment.

#### **3.2 Specific Criteria**

**Summary of Inclusion criteria:** 1) Age  $\geq$ 70 year; 2) Eligible CVD diagnosis (hospitalization or acute event for AMI/ACS, stable CAD, revascularization [CABG, PCI], valvular heart disease [specifically, surgical or percutaneous intervention for mitral regurgitation or aortic stenosis], PAD or HF [exacerbation or new diagnosis]); 3) English speaking and able to provide informed consent; 4) able to be assessed and undergo study interventions.

**Summary of exclusion criteria:** 1) Unstable medical condition as indicated by history, physical exam, and/or laboratory findings; 2) Presence of non-CVD conditions likely to be fatal within 12 months (e.g., metastatic cancer); 3) Severe cognitive impairment: Short Blessed with a score of 13 or greater, or cannot consent (as indicated by medical record); 4) Long-term care resident at admission with no plans to return to independent living; 5) anticipates inability to return for required reassessments.

#### **3.3 Special Populations**

Vulnerable populations (fetuses, pregnant women, children, prisoners, and institutionalized persons) and adults unable to consent will not be included in this study.

[figure not shown]
### **4.0 Multi-Site Research**

The University of Pittsburgh will serve as the coordinating site.

### **5.0 Study Timelines**

- *Duration of an individual subject's participation in the study:*  
Each participant's participation in the study will last between approximately 26-52 weeks, depending on their time of enrollment into the study. The goal will be for as many participants to reach 52 weeks as the time of the study allows. Starting during inpatient hospitalization or within 90 days after an acute event and following the participants for approximately 26-52 weeks from enrollment.
- *The duration anticipated to enroll all study subjects:*  
We anticipate that we will enroll all study subjects over approximately 24 months.
- *The estimated date for the investigators to complete this study (complete primary analyses):*  
We anticipate that we will complete data collection over approximately 52 months as indicated in the study timeline below.

## Study Timeline

## 6.0 Study Endpoints

### 6.1 Primary and secondary study endpoints.

All eligible and consenting patients will undergo a standard battery of assessments at baseline and after approximately 3, 6, and 12 months (12 months as the study length allows). Assessors will be blinded regarding each patient's group assignment.

Aim 1: to test relative benefits of the MACRO vs. SOC arms, comparing (a) differences in the AM-PAC CAT Basic Mobility Domain (primary outcome; primary endpoint 3 months), as well as (b) complementary functional/qualitative metrics accelerometry, AM-PAC CAT Daily Activity Scale, depression, frailty, self-efficacy, and quality of life; (c) differences in participation, and adherence; (d) readmissions and hospitalization.

[figure not shown]
In Aim 2, assessments in physical activity (accelerometry); AM-PAC CAT Daily Activity Domain; depression; frailty; self-efficacy; and quality of life will be repeated at approximately 6 and 12 months (12 months as the study length allows) to evaluate longer term impact of the MACRO intervention vs. SOC.

In Aim 3, moderator analyses will examine characteristics of patients to identify those most likely to benefit from a MACRO intervention.

## 7.0 Procedures Involved

### 7.1 Study design.

**Overview and summary of design:** This is a pragmatic randomized controlled trial (RCT) of 374 older adults, with 40 subjects at the University of Pittsburgh, eligible for CR: hospitalized adults aged  $\geq 70$  years with a primary diagnosis of AMI/ACS, stable IHD, CABG, PCI, valvular heart disease (valve replacements or repairs for aortic stenosis or mitral regurgitation), PAD or HF. Patients who consent to participate will be randomly assigned to MACRO or SOC arms (which may include CR at the discretion of the providers) (Figure below). In the MACRO arm, patients will benefit from personalized engagement and CR will be explicitly facilitated, enhanced, tailored to patients' preferences and needs, and utilizing a flexible range of options (site-, home, or hybrid). In comparison, SOC provides no specialized engagement, and no programmatic facilitation, enhancement, customization, or deliberate flexibility in how care is provided.

## A. Data collection overview

B. Table 1 shows outcome measures planned at each time point.

**Table 1. Data Collection Plan**

Study Measure	Baseline	3, 6, 12 months
Risk assessment	X	
AM-PAC CAT Basic Mobility Domain (primary outcome)	X	X
Accelerometer	X	X
AM-PAC CAT Daily Activity Domain	X	X
3 Day Food Record (not at WU site)	X	X
Questionnaires	X	X
CR adherence/attendance		X
Reduced falls, medication burden, readmissions and hospitalization	X	X

## 7.2 Research procedures.

### Assessments

Assessments will occur at some or all of the following time points: baseline (while inpatient or up to approximately 90 days following an acute event), and 3, 6, 12 months (12 months as study length allows) post-randomization. Assessments can be completed in-person (at facility), by telephone or video call.

Assessments are outlined below:

- A. **Cognitive function.** Short Blessed (score  $\geq 13$ ) will be used as an initial screening tool to rule-out severe cognitive impairment.
- B. **Depression:** Patient Health Questionnaire 9-item (PHQ-9). Older adults eligible for CR have high rates of depressive symptoms that amplifies vulnerability to disability. Mitigating depressive symptoms is an important rehabilitation outcome. The PHQ-9 is a simple, pragmatic instrument that is well-validated and responsive to change. A score of 10 or greater indicates depression symptoms. For all patients with PHQ-9  $\geq 10$  who are not receiving treatment for their depression already, we will consult [name] and also notify their primary provider (as needed) to enable follow-up and greater safety. If a participant expresses or demonstrates suicidal ideation, standard of policy of the local hospital for suicide risk will also be followed.
- C. **Readiness for Change:** Interventions like CR that require active engagement by participants are often dependent on the participant's willingness to adopt new activities, habits and routines. The TTM is a behavioral framework for understanding readiness for change through 5 change-stages: (1) precontemplation, (2) contemplation, (3) preparation, (4) action, (5) maintenance. In studies examining patient-centered interventions with community-dwelling older adults, increased readiness for change was associated with a 62% greater likelihood of goal attainment.
- D. **AM-PAC-CAT:** The AM-PAC is an activity limitations measure. This measure is picked as an important complement physical assessment measures both as a self-reported index, and because it clarifies relative degrees of capacity amidst the heterogeneity anticipated in this population (i.e., frail

to robust). AM-PAC allows for the examination of perceived difficulty and level of assistance/limitations in 3 domains – Basic Mobility (**primary outcome**), Daily Activity, and Applied Cognition, building on Item Response Theory (IRT). AM-PAC- combines items from existing instruments into one scale, and ranks them according to level of difficulty for each of the 3 domains. IRT assumes that all items within a domain measure a single concept and are independent. In this study the Basic Mobility domain will be the primary outcome, and the Daily Activity domain will be one of the secondary outcomes.

- E. **Self-efficacy:** Higher self-efficacy correlates to greater capacity and duration for physical activity and independence. For this study we rely on the 13-item self-efficacy scale developed by Sullivan, et al.
- F. **Quality of Life (QoL):** RAND-12 is a 12-item scale developed to evaluate QOL.
- G. **Falls:** Falls are a common, deleterious, and expensive aspect of aging which may be preventable via the tenets of MACRO such as good transitional care, age-appropriate exercise, and de-prescribing. We will measure falls as follows: at baseline, we will ask, “Have you had any falls in the past 3 months?” In follow-up assessments, we will ask about interim falls, as well as their severity (e.g., if they caused injury).
- H. **Deprescribing-Eligible Medications (DEMs):** DEMs are medications that are potentially deleterious for participants. These medications are pre-identified, based in part on the Beers Criteria and in part based on CR-specific risks of falls.
- I. **Readmissions:** At follow-up assessments, we will ascertain whether the participant had any hospital admissions or other care (e.g., ER visits).
- J. **Institutionalization:** At follow-up assessments, we will ascertain whether the participant required a brief or long-term institutionalization (e.g., Assisted Living, Skilled Nursing Facility [SNF] or inpatient rehabilitation).
- K. **Physical activity.** Physical activity will be measured in all participants at each assessment for approximately 7-10 days using the ActiGraph accelerometer. Participants are asked to wear the ActiGraph on their wrist for 7-10 days, removing it only for times when the arm will be submerged in water for long periods of time like swimming. After 7-10 days, participants will mail the accelerometer back to the study team in a stamped, pre-addressed envelope provided to them at their study visit, or they will bring it with them to their next scheduled visit. We may also contact participants by telephone to ensure monitors are returned.
- L. **Adherence to the cardiac rehabilitation program.** An assessment of the total number of CR sessions participants complete will be tracked via telephone calls, collection of data from the onsite cardiac rehabilitation programs, and/or self-report by participants at the completion of the study.
- M. **Risk Assessment.** The aggregate risk of each participant will be assessed at baseline. We will assess risk across three domains: medical, functional, and psychosocial. An assignment of high, moderate, or low risk will be determined using the participants’ scores on various baseline assessments.

- N. **Duke Activity Status Index (DASI)** is a 12-item scale that has been validated in cardiac patients against peak VO2 and has been demonstrated to be a reliable and responsive tool to quantify physical activity in daily living.
- O. **FRAIL Scale.** A five-item scale frailty assessment that assesses Fatigue, Resistance, Ambulation, Illnesses, and Loss of weight that can be administered over the phone.
- P. **Rapid Estimate of Adult Literacy (REALM-SF).** (optional as now contingent on COVID-19 risk) Will be utilized to evaluate health literacy on all participants.
- Q. **Nutrition:** Will be assessed with the Rapid Eating Assessment for Participants short (REAP-S) (to be collected at all sites) and a 3-day food record (not collected at WU site). REAP-S is a 16-item questionnaire to assess eating habits for patients. A 3-day food record allows will also be collected to assess quantities of specific food groups (such as protein).

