C. **Statistical Analyses.** Overview-We will perform all main analysis based on intention-to-treat philosophy following the a priori plans outlined below. All statistical analyses will be performed and overseen by the study statistician [name] using SAS® version 9 (SAS Institute, Inc., Cary, North Carolina). Participant flow will be summarized using a CONSORT diagram. Data will be summarized by treatment group and time point as well as baseline to follow-up change using appropriate descriptive statistics. First, the baseline participant characteristics will be compared between the two arms. Any significant differences will be noted and accounted for as additional covariates in the sensitivity analyses. Second, main analyses to address the aims will be performed as outlined below. Confirmatory hypothesis testing will be performed using multiple imputation for missing data. Third, a set of sensitivity analyses including additional covariates and ignoring missing data will be performed to evaluate the robustness of our findings.

**Baseline Comparisons**-Due to the randomization scheme balanced with respect to study site and the large sample size, it is unlikely that other baseline participant characteristics will be significantly different between the arms. However, we will control for any participant characteristics that are found to be significantly different by including them as additional covariates in the sensitivity analyses. In such an event, we will not alter the primary analytic strategy to preserve its a priori nature and predictability. We will use independent samples *t*-, Wilcoxon rank sum, chi-square and Fisher's exact tests, as appropriate based on distributional properties, and continuous/categorical nature of the characteristic being compared.

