**Aim 1 Analysis**-We will fit a series of linear mixed models using the SAS® MIXED procedure with baseline to follow-up changes in continuous outcomes as the dependent variable; intervention arm (MACRO/SOC), follow-up time point (3/6/12 months) and their interaction term as the fixed effects of interest; the baseline value of the continuous outcome as a fixed effect covariate; and a participant random effect to account for multiple measurements over time from the same participant. We will appropriately construct means contrasts to estimate MACRO vs SOC at each follow-up time point. The magnitude and statistical significance at  $\alpha=0.05$  of the MACRO vs SOC difference at 3 months for AM-PAC CAT Basic Mobility Domain will serve as the formal test of the primary hypothesis H1.1. If significant, we will define a meaningful responder as having at least a 2.60 point improvement in AM-PAC CAT Basic Mobility Domain over 3 months, compute percentage of responders in both arms, and conclude a number-needed-to-treat (NNT) as the reciprocal of the difference in percentages. We will employ the same analytic strategy described above for each of our secondary continuous outcomes such as physical activity, depression, frailty, self-efficacy and quality of life (H1.2). For the secondary outcomes measured only once at 3 months such as participation, adherence and satisfaction (H1.3), we will consider using Wilcoxon rank sum, chi-square and Fisher's exact tests to make between-intervention comparisons, depending on the categorical/ordinal/interval nature of the outcomes and their propensity for ill-behaved distributional properties. For count outcomes such as falls, number of medications, readmissions and hospitalizations in H1.4, we will fit a series of negative binomial regression models with the count outcome as the dependent variable; exposure time for the counts as an offset; a log link function; and intervention arm as the main independent factor of interest; and a marker of history of the outcome at baseline as a covariate MACRO vs SOC incident rate ratio and its statistical significance will serve as tests of H1.4.

**Aim 2 Analysis**-In the linear mixed models described above for H1.1 and H1.2, we will examine the between-intervention means contrasts at 6- and 12-months. The magnitude and statistical significance of the MACRO vs SOC arm differences at 6 and 12 months will serve as the formal test of the hypothesis H2.1.

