#### D. Sample Size and Power.

**Sample Size Justification.** We base our sample size on published data, published statistical methods, and commercially available software (SAS® POWER procedure; SAS Institute, Inc., Cary, North Carolina). Between-subject standard deviation of the baseline to follow-up change in the primary outcome AM-PAC CAT Basic Mobility Scale is approximately 7.97 in rehabilitation outpatients. We consider 2.60 points a minimally clinically important difference based on MDC68. We plan to randomize 187+187=374 participants, anticipating 149+149 completers assuming a conservative 80% retention rate. We can detect a between treatment arm difference of 2.60 points in AM-PAC CAT Basic Mobility Scale with 80% statistical power in a two-tailed test at  $\alpha=0.05$ . This difference is smaller than the actual observed changes previously reported, indicating ample statistical sensitivity. The logistic regression model proposed in Aim 3 requires a minimum of about 5-10 events per variable, and assuming a half in the MACRO group responds, we would be able to fit a multivariable model with at least 15 variables. Thus, we are confident of the adequacy of sample size to address all aims.

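### Baseline mobility may be measured in hospital or up to about 90 days after the event, but the primary model adjusts only for the baseline score, so some precision is probably forgone

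*Combined protocol and SAP*

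**What the plan says.** Section 7.2 (Assessments) sets the window as "baseline (while inpatient or up to approximately 90 days following an acute event", with later visits at 3, 6 and 12 months counted from randomization. Section 5.0 gives the same window: "Starting during inpatient hospitalization or within 90 days after an acute event".

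The Aim 1 analysis in section 9.1 models change from baseline. Its terms are arm, "follow-up time point (3/6/12 months) and their interaction term as the fixed effects of interest", then "the baseline value of the continuous outcome as a fixed effect covariate", and a participant random effect. Neither inpatient status nor time since the event is listed.

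Randomization (section 3.1 B) is stratified by site, and "no other stratification criterion will be employed". For other baseline characteristics, section 9.1 says: "Any significant differences will be noted and accounted for as additional covariates in the sensitivity analyses". If that happens, "we will not alter the primary analytic strategy to preserve its a priori nature and predictability". The Aim 3 subgroups do not use setting or timing either.

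**The concern.** Because the 3-month visit is timed from randomization, a participant enrolled in hospital contributes change over roughly days 0 to 90 after the event. One enrolled near the end of the window contributes change over roughly days 90 to 180. Expected spontaneous recovery probably differs between these two stretches, and the setting of the baseline assessment is fixed before treatment starts.

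The baseline score captures part of this difference. With a single slope for everyone, however, a low score from acute illness and an equally low score from lasting limitation receive the same predicted change. Whatever setting still predicts stays in the residual and widens the interval for the arm difference. Setting is also not stratified, so a chance imbalance between arms would carry through to the primary estimate. The stake is efficiency in a trial sized at 80% power with almost no margin.

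**Working it through.** **Inputs from section 9.1 D:** SD of change 7.97 (rehabilitation outpatients), difference 2.60, two-sided α = 0.05, 149 completers per arm, 187 per arm randomized.

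**1. The plan's own figure.** Normal approximation: n = 2 × (7.97/2.60)² × (1.960 + 0.842)² ≈ 147.5, so 148 per arm. The two-sample t calculation gives 148.5, so 149. Then 149/0.80 = 186.25, so 187 per arm and 374 in total. Power at 149 per arm is 80.1% by t (80.4% by the normal approximation). The stated figure reproduces, and it does so without setting or timing as covariates.

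**2. Power if the covariates are added.** Let R² be the share of the variance remaining after the baseline score that setting and timing explain. Residual SD = 7.97 × √(1 − R²), SE = SD × √(2/149), and power is from the two-sample t test. Equivalent extra completers per arm = 149/(1 − R²) − 149. As a simplification, 7.97 is used as the residual SD, as the plan's power statement does. R² is assumed, because the documents give no value.

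| Assumed R² | Residual SD | SE | Power | Equivalent extra completers per arm |
|---|---|---|---|---|
| 0% | 7.97 | 0.923 | 80.1% | 0 |
| 2% | 7.89 | 0.914 | 80.9% | 3 |
| 5% | 7.77 | 0.900 | 82.1% | 8 |
| 10% | 7.56 | 0.876 | 84.1% | 17 |

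**3. How large R² might be after baseline adjustment.** Illustrative assumptions: half the baselines are inpatient; inpatients carry a temporary deficit of d points that resolves by 3 months; the within-setting SD s is the same at baseline and 3 months; the within-setting SD of change is 7.97. Take s = 10 and d = 5.

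- Within-setting correlation: ρ = 1 − 7.97²/(2 × 10²) = 0.682.
- Gap between settings at equal baseline score: ρ × d = 3.41 points.
- Residual variance within setting: 10² × (1 − 0.682²) = 53.4.
- Variance of the inpatient indicator not explained by the baseline score: 0.25 × (1 − 6.25/106.25) = 0.235.
- Share: 0.235 × 3.41² = 2.74, and 2.74/(53.4 + 2.74) = 4.9%.

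For s from 8 to 12, the share is 1–2% at d = 3, 3–6% at d = 5 and 6–13% at d = 8. This is for setting alone.

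**4. Sensitivity to the inpatient share.** For a residual gap D and inpatient share q, R² = q(1 − q)D²/7.97². With D = 2.5 and a 50/50 split, R² is 2.5% (power 81.1%). With D = 5 and a 10/90 split it is 3.5% (81.5%). With D = 2.5 and 10/90 it is 0.9% (80.5%).

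**5. Chance imbalance.** With a 50/50 mix, the 1.96-SE limit on the between-arm difference in inpatient share is 1.96 × √(0.25 × 2/149) = 11.4 percentage points. With the 3.41-point gap from step 3, that moves the estimate by about 0.39 points, or 15% of 2.60.

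**6. If 7.97 holds only within a setting.** Mixing settings 50/50 without adjustment gives SD = √(7.97² + 0.25 × D²). For D = 2.6 this is 8.08 (power 79.1%), and for D = 5.2 it is 8.38 (76.1%).

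**The case against.** The strongest reply is that nothing in the plan is wrong. Its power claim, "We can detect a between treatment arm difference of 2.60 points in AM-PAC CAT Basic Mobility Scale with 80% statistical power", reproduces without these covariates, and randomization protects the arm contrast from systematic bias. The baseline score is already in the model and should absorb part of any difference in recovery stage. Section 7.1 describes hospitalized adults, so an even split between settings cannot be presumed; with few participants in one setting the gain shrinks. The plan also has a route for imbalance, through sensitivity analyses. All of this stands, and it limits the point to an efficiency gain of uncertain size.

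Time since event is a further difficulty. Stable coronary disease and PAD are eligible, and recruitment includes clinics and self-referral, so some participants may have no clear index event. Table 1 lists neither event date nor baseline setting. It therefore cannot be said that both variables are known for everyone or already collected.

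A reader might infer that recovery stage is a large, established source of variance, that precision is certainly lost, or that the trial is underpowered. The documents support none of these: they report no association of setting or timing with 3-month change.

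The reply does not dispose of the point. The sensitivity route opens only after a significant baseline difference and never touches the primary estimate. An imbalance too small to reach significance can still shift the result if the variable is prognostic. Naming the covariate in advance keeps the a priori character that the plan wants to protect.

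**Conclusion.** The point holds as a modest, conditional improvement. The primary analysis omits a baseline characteristic that is probably prognostic for 3-month change, so it probably forgoes some precision and leaves chance imbalance in setting uncorrected in the primary estimate. It does not introduce systematic bias, and the stated 80% power is not wrong.

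For an assumed 0–10% of remaining variance explained, the gain in power runs from nil to 4 percentage points. A temporary inpatient deficit of 3 to 5 points with an even split implies about 1–6% from setting alone. The gain could be close to zero if the baseline score absorbs most of the effect or if nearly all baselines are taken in one setting. The inpatient share, the baseline SD and the size of the deficit are all assumptions, since the documents give none of them.

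**What to change.** Before unblinding, add to the Aim 1 analysis in section 9.1 that baseline setting (inpatient yes/no) and its interaction with visit are prespecified fixed effects in the primary AM-PAC Basic Mobility model and in the other continuous-outcome models. Include them whether or not the arms differ significantly on setting.

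Add days from index event to baseline only with a written definition of the index event and a rule for participants without one, for example a separate no-acute-event category.

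The cost is a few degrees of freedom out of about 298 completers, plus recording the baseline setting and the event date used to confirm the 90-day window. No extra participants or visits are needed. The downside is that the gain may turn out to be small.
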